2. STUDY OBJECTIVES

The purpose of this study is to provide data on the safety and efficacy of FS VH S/D 500 s-apr compared to DuraSeal Dural Sealant as an adjunct to sutured dural closure in patients who are undergoing elective cranial surgery for the treatment of a pathological condition (eg, benign/malignant tumours, vascular malformations, or Chiari type 1 malformations) specifically in the PF or ST region.

2.1 Primary Objective

The primary objective of this study is to evaluate the efficacy of FS VH S/D 500 s-apr compared to DuraSeal Dural Sealant as an adjunct to sutured dural closure.

2.2 Secondary Objective

The secondary objective of this study is to evaluate the safety of FS VH S/D 500 s-apr compared to DuraSeal Dural Sealant as an adjunct to sutured dural closure.

3. INVESTIGATIONAL PLAN

3.1 Overall Study Design and Plan

This study is a Phase 3, prospective, controlled, randomised, single-blind (patient), multicenter study to evaluate the safety and efficacy of FS VH S/D 500 s-apr compared to DuraSeal Dural Sealant as an adjunct to sutured dural closure in a total of 202 evaluable patients undergoing elective cranial surgery for the treatment of a pathological condition (i.e., benign/malignant tumours, vascular malformations, or Chiari type 1 malformations) specifically located in the PF or ST region.

Eligibility according to general and intra-operative criteria will lead to the final selection of the patient into the study, which is determined by the presence of an intra-operative CSF leak after primary dural closure with sutures. Upon detection of CSF leak, the patient's randomisation assignment to either IP (FS VH S/D 500 s-apr) or to control (DuraSeal Dural Sealant) stratified by center and surgical regions (PF or ST) will be applied.

3.2 Overall Study Design

[figure not shown]
Patients who are ≥ 18 years of age who sign the informed consent (IC) and who meet all pre-operative inclusion/exclusion criteria will undergo elective cranial surgery with either craniotomy or craniectomy with planned durotomy. Their eligibility for surgery will be evaluated on the basis of the routine medical work-up (medical history, physical examination/review of systems, laboratory, imaging) and of the screening results for general inclusion and exclusion criteria (Section 4.2) during the ≤ 30 -day period prior to surgery.

For a schematic diagram of intra-operative study design, see [Figure 1](#). During surgery (Day 0), patients will be evaluated according to intra-operative inclusion and exclusion criteria for further eligibility (Section 4.3); if eligible, patients will be evaluated upon completion of the primary suturing of the dura. Only if an intra-operative CSF leak is observed (spontaneous CSF leak or CSF leak after Valsalva manoeuvre; 25 cm H₂O for up to 5 - 10 seconds), the patient's randomisation assignment to 1 of 2 treatments – repair with FS VH S/D 500 s-apr or DuraSeal Dural Sealant as an adjunct to dural closure – will be applied. Patients with no intra-operative CSF leak will not be enrolled in the trial (ie, defined as screen failures).

See [Appendix 1](#) (Schedule of Procedures and Assessments).

Figure 1. Intra-operative Study Design

3.3 Rationale for Study Design and Control Group

With the specific properties of liquid FS VH S/D 500 s-apr (ie, tissue adhesion, sealing, wound healing) when combined with appropriate suture techniques, the potential benefit in the creation of a watertight suture line in the dura mater for patients undergoing neurosurgery seems logical and clinically relevant. Though current and previous generations of FS VH S/D 500 s-apr have been used extensively as an adjunct to suturing in dural repair for many years, this study will compare the use of FS VH S/D 500 s-apr to the use of DuraSeal Dural Sealant as an adjunct in dural repair. Additionally, the European Guideline on Core SmPC for Plasma-derived FS/Haemostatic Products requires clinical data to support any indication for the sealing of the dura suture line during cranial surgery.²⁵

The only clinical study data for FS VH S/D 500 s-apr is from a small randomised controlled trial (RCT) pilot study (N = 62) conducted by Baxter, where FS VH S/D 500 s-apr was used to augment the closure of a dura defect by suturing in a patch of autologous fascia, pericranium or suturable collagen-based dura substitute, which was the standard of care. The primary endpoint was the incidence of post-operative CSF leak at 33 days post-operatively. The results demonstrated no disadvantage with adding FS VH S/D 500 s-apr to the standard of care; safety was also shown to be comparable to standard of care. During this study, cranial surgery was specifically located in the PF region. CSF leakage after primary dura sutures was excluded. It is important to note that though the results demonstrated no disadvantage using FS VH S/D 500 s-apr as a sealant, the study was very small and likely underpowered to demonstrate any superiority effect; thus the study was considered inconclusive. However, FS VH S/D 500 s-apr was demonstrated to be safe for neurosurgery.

Recently, a large (n = 139) and well-powered RCT was conducted. The RCT evaluated a similar FS product, containing the same main active ingredients (fibrinogen and thrombin) as FS VH S/D 500 s-apr; this study proved superiority of another FS over the control treatment (sutures only) in providing a watertight dural closure during surgery.²⁶ The safety profile was comparable in the 2 groups and, with this trial, an indication for “suture line sealing in dura mater closure” was obtained in the EU.

Baxter believes that FS VH S/D 500 s-apr will perform equivalently to the DuraSeal Dural Sealant when used as an adjunct to suturing during surgery. While other clinical designs were discussed, the design chosen seems appropriate, as it provides a reasonably accurate reflection of the typical usage of FS in clinical practice.

3.4 Study Duration and Dates

The overall duration of the study is expected to be 26 months from study initiation (ie, first patient enrolled) to study completion (ie, last patient last visit). The recruitment period is expected to be 24 months.

The patient participation period is from pre-operative screening to Day 60 (± 3 days) after surgery (ie, last study visit), unless prematurely discontinued.

Day of surgery is defined as Day 0. Scheduled Follow-up visits ([Appendix 1](#)) will take place on the day before discharge or on Day 5 (± 2 days), whichever is first, Day 30 (± 3 days), and on Day 60 (± 3 days) after surgery (last study visit). Follow-up visits will be advanced if complications occur prior to the scheduled date. According to clinical

experience, the incidence of CSF leaks are rare, however when they do occur the majority are detected within 60 days. Therefore, the follow-up period is deemed appropriate.

Patients are strongly encouraged to contact or visit the study site without delay to discuss a perceived AE that occurs after the first Follow-up visit and between the scheduled Follow-up visits, and to follow the directives of the study site for appropriate action (Unscheduled Follow-up visit assessments, see [Appendix 1](#)).

See schematic study overview including the study visits (Days 0, 5, 30, and 60) in [Appendix 1](#).

4. STUDY POPULATION SELECTION

4.1 Study Population

Approximately 476 patients will be screened in order to randomise approximately 224 patients (with a minimal number of 56 PF procedures) and have 202 evaluable patients age ≥ 18 years, both genders, who are to undergo elective craniotomy/craniectomy for pathological processes (eg, benign or malignant tumours, vascular malformation, or Chiari type 1 malformations) in the PF or ST region and who have persistent CSF leakage following the primary attempt at suture closure of the dural incision. Randomisation will be stratified by study center and surgical region (PF or ST) and will be aimed to achieve an approximate 3:1 ratio (ST:PF) of the 2 surgical regions in the randomised study population. The minimal number of PF procedures will be approximately 56.

We have estimated a ████ % screen failure rate, based on published literature, using a similar method to detect CSF leaks during cranial surgery.²⁷

The study will be conducted in 4 countries (US, Spain, Germany, and Czech Republic). Additional countries may be involved in the trial.

4.2 Inclusion and Exclusion Criteria (General)

The general inclusion criteria (1 - 5) and the general exclusion criteria (1 - 20) are to be evaluated before each patient undergoes planned surgery. Only patients who meet the general inclusion criteria and do not meet the general exclusion criteria are to be evaluated further according to the intra-operative inclusion and exclusion criteria Section 4.3.

4.2.1 Inclusion Criteria (General)

Each patient must meet the following criteria to be enrolled in this study. Any patient not meeting all the inclusion criteria will be regarded as a screen failure.

1. Patients ≥ 18 years of age undergoing craniotomy/craniectomy for pathological processes in the PF or ST region
 2. Patients must be willing and able to participate in the study and provide written IC before any protocol specific assessment is performed
 3. Patients must be willing to receive peri-operative antibiotic prophylaxis
 4. Female patients of childbearing potential must present with a negative serum pregnancy test, and must agree to employ adequate birth control measures
-
-

[restricted to abstinence, barrier contraceptives, intrauterine contraceptive devices or licensed hormonal products] for the duration of their participation in the study

5. Patients are willing and able to comply with the requirements of the protocol

4.2.2 Exclusion Criteria (General)

Each patient must not meet the following criteria to be enrolled in this study. Any excluded patient will be regarded as a screen failure.

1. Patients with a dural lesion from a recent surgery that still has the potential for CSF leakage
 2. Patients who had undergone chemotherapy treatment, excluding hormonal therapy, within 3 weeks prior to the planned procedure, or with chemotherapy scheduled within 7 days following surgery
 3. Patients with radiation therapy to the surgical site or standard fractionated radiation therapy scheduled within 7 days following surgery
 4. Patients with a previous craniotomy/craniectomy within 6 months prior to the study surgery
 5. Use of corticosteroids on a chronic basis (defined as daily use of corticosteroids for ≥ 8 weeks) for purposes other than decreasing the symptoms of systemic chemotherapy (unless if those steroids were discontinued 4 weeks prior to the planned surgery)
 6. Patients with a known hypersensitivity to the components of the IP or control (human fibrinogen, synthetic aprotinin, human albumin, human FXIII, tri-sodium citrate, histidine, niacinamide, polysorbate 80, human thrombin, polyethylene glycol [PEG], trilycine amine)
 7. Patients with a known hypersensitivity to US Federal Drug & Cosmetic Blue #1 dye
 8. Evidence of an infection indicated by any one of the following: clinical examination supporting the diagnosis of infection, fever (temperature $>100.7^{\circ}\text{F}$ or 38.2°C), positive urine culture, positive blood culture, positive chest X-ray consistent with pulmonary infection, or infection along the planned surgical path. A white blood cell (WBC) count of <20000 cells/ μL is permitted if the patient is being treated with steroids in the absence of all other infection parameters
-
- 

9. Female patients of childbearing potential with a positive pregnancy test or intent to become pregnant during the clinical study period
10. Female patients who are nursing
11. Patients with exposure to another investigational drug or device clinical trial within 30 days prior to enrolment or anticipated in the 60-day Follow-up period
12. Patients with severely altered renal function as confirmed by local laboratory reference ranges for serum creatinine and/or hepatic function (alanine aminotransferase [ALT], aspartate aminotransferase $>3 \times$ upper limit of normal [ULN])
13. Patients who currently have or have had a compromised immune system (such as Acquired Immune Deficiency Syndrome [AIDS]) or autoimmune disease, or were on chronic immunosuppressant agents
14. Patients with uncontrolled diabetes as evidenced by the institution's standard of care (glycated haemoglobin [HbA1c] $>7\%$, blood glucose, etc.)
15. Patients with traumatic injuries to the head
16. Patients with dural injury during craniotomy/craniectomy that cannot be eliminated by widening the craniotomy/craniectomy to recreate the native dural cuff
17. Patients requiring surgical approaches that would not allow sutured dural closure such as trans-sphenoidal or translabyrinthine/-petrosal/-mastoid. Superficial penetration of mastoid air cells is allowed
18. Patients with hydrocephalus, except occlusive hydrocephalus caused by PF pathology or incompletely open cerebrospinal fluid pathways, to be treated during surgical procedure
19. Existing CSF (ventricular, etc.) drains, Cushing/Dandy cannulation, or Burr holes which damage the dura
20. Patients with confined bony structures where nerves are present and neural compression may result due to swelling

4.3 Inclusion and Exclusion Criteria (Intra-operative)

The intra-operative inclusion criteria (1 - 3) and the intra-operative exclusion criteria (1 - 9) will be evaluated when the patient is in surgery.

4.3.1 Inclusion Criteria (Intra-operative)

1. Patients with surgical wound classification Class I ([Appendix 3](#))
2. The cuff of native dura along the craniotomy edge on each side is adequate, based on surgeon's judgment, to facilitate suturing and to allow for sufficient surface area for adherence of the IP
3. Patient's CSF leak was present intra-operatively following completion of primary dural closure (with or without non-autologous duraplasty or autologous tissue); either spontaneously or upon Valsalva manoeuver (25 cm H₂O for up to 5 - 10 seconds)

4.3.2 Exclusion Criteria (Intra-operative)

1. Patient has a gap between durotomy edges of >2 mm after primary dural closure in the judgment of the investigator
2. Patients requiring the use of implants made of synthetic materials coming into direct contact with dura
3. Patient has 2 or more separate dural defects
4. Patients with intersecting durotomy scars in the surgical path from a previous operation that cannot be completely removed by the planned dural resection
5. Placement of Gliadel Wafers
6. Major intra-operative complications that require resuscitation or deviation from the planned surgical procedure
7. Patients in whom application of the Valsalva manoeuver is not found appropriate due to increased safety risk
8. Patients requiring the use of other FSs or PEG-based sealants
9. Patients with any other intra-operative findings identified by the surgeon that may preclude the conduct of the study procedure

4.4 Removal of Patients from Therapy, Assessment, or Study

Any patient may voluntarily withdraw (ie, reduce the degree of participation in the study) consent for continued participation and data collection. The reason for withdrawal will be recorded on the End of Study electronic case report form (eCRF). Assessments to be performed at the termination visit (including in cases of withdrawal or discontinuation) are described in [Section 6.16](#) and [Section 7.6](#).

Discontinuation (ie, complete withdrawal from study participation) may be due to drop out (ie, active discontinuation by patient) or loss to follow-up (ie, discontinuation by patient without notice or action). Additionally, the investigator and the sponsor have the discretion to discontinue any patient from the study if, in their judgment, continued participation would pose an unacceptable risk for the patient.

The data safety monitoring board (DSMB) will upgrade an AE to a serious adverse event (SAE) if the AE results in a patient injury that: jeopardizes the patient and may require medical or surgical intervention, prolongs the hospitalization, requires intervention to prevent permanent impairment or damage, causes disability or permanent damage, causes a congenital anomaly/birth defect, is life-threatening, or results in death.

The study enrolment will be paused and re-evaluated by the DSMB if:

- 2 or more SAEs occur in the same patient and are directly related to the investigational product, across 10 patients, or
- 20 aggregate SAEs occur that are directly related to the investigational product, or
- 1 patient death occurs that is directly related to administration of the investigational product.

The DSMB is required to define the rule(s) appropriate to restart the study, if the above triggering events occur during study conduct.

Discontinuation may also be due to the Institutional Review Board/Independent Ethics Committee (IRB/IEC) or Competent Authority's decision to terminate or suspend approval of the study or the investigator.

5. STUDY TREATMENTS

5.1 Enrolment, Randomisation, and Assignment to a Treatment Group

This is a randomised, single-blind (patient), controlled clinical study. In order to minimize/avoid bias, patients will be randomly assigned to 1 of 2 treatments: IP (FS VH S/D 500 s-apr) OR control (DuraSeal Dural Sealant) with a 1:1 ratio stratified by center and surgical regions (PF or ST).

5.2 Randomisation

Patients will be randomly assigned to FS VH S/D 500 s-apr or DuraSeal Dural Sealant at a ratio of 1:1. Randomisation will be stratified by study center and surgical region (PF or ST) with the goal of achieving an approximate 3:1 ratio (ST:PF) of the 2 surgical regions in the randomised study population. Randomisation will be controlled via an interactive Web-response system (IWRS), [REDACTED] using dynamic allocation. On the day of surgery (Day 0), upon confirmation of pre-operative eligibility criteria, a member of the site study staff other than the surgeon will obtain a treatment assignment from the IWRS. Adequate amounts of FS VH S/D 500 s-apr and DuraSeal Dural Sealant will be taken into the operating room for potential use as the study treatment.

Immediately after the patient's intra-operative eligibility for study treatment has been confirmed (ie, spontaneous CSF leak or CSF leak after Valsalva manoeuvre), the assigned treatment will be revealed to the surgeon and the assigned IP or control will be applied to the CSF leak site. Following surgery, the treatment assignment and the actual treatment applied will be entered in the eCRF for the patient.

If the patient's eligibility is not confirmed intra-operatively, the operation will be performed according to hospital standards. The study site designee will document the noncompliant criterion or criteria plus the date and reason(s) for the patient's exclusion in the eCRF, and an entry will be made in the IWRS that the study treatment was not administered.

Details of the IWRS and its use will be described in a separate IWRS instruction manual that will be maintained in the trial master file and in each center's investigator trial file.

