To evaluate the safety of FS VH S/D 500 s-apr compared to DuraSeal Dural Sealant as an adjunct to sutured dural closure.

Study Design:

This study is a Phase 3, prospective, controlled, randomised, single-blind (patient), multicenter study to evaluate the safety and efficacy of FS VH S/D 500 s-apr compared to DuraSeal Dural Sealant as an adjunct to sutured dural closure in a total of 202 evaluable patients undergoing elective cranial surgery for the treatment of a pathological condition (eg, benign/malignant tumours, vascular malformations, or Chiari type 1 malformations) specifically located in the posterior fossa (PF) or supratentorial (ST) regions.

Eligible patients will sign an informed consent (IC), and undergo elective cranial surgery of the PF or ST region with either craniotomy or craniectomy with planned durotomy. During the surgery, the patients will be evaluated according to intra-operative inclusion/exclusion criteria for further eligibility. If eligible, the patients will be evaluated upon completion of the primary suturing of the dura (with or without non-autologous duraplasty or autologous tissue). Only if intra-operative cerebrospinal fluid (CSF) leak is confirmed (spontaneous CSF leak or CSF leak after Valsalva manoeuvre; 25 cm H₂O for up to 5 - 10 seconds), the patient will be randomised to treatment with either FS VH S/D 500 s-apr or DuraSeal Dural Sealant (control) in a 1:1 allocation ratio stratified by center and surgical regions (PF or ST). After treatment, a final assessment for intra-operative CSF leak (spontaneous CSF leak or CSF leak after Valsalva manoeuvre) will be conducted to evaluate the intra-operative watertight dura closure.

Two applications of the study products are allowed. In the event that 2 applications are used, the Valsalva manoeuvre must be repeated. In the case of continuous intra-operative CSF leak at the final assessment, a rescue therapy for sealing any CSF leaks may be applied according to the surgeon's choice/institutional practice (eg, other fibrin sealants [FSS] except FS VH S/D 500 s-apr or DuraSeal Dural Sealant).

Study Population:

Approximately 476 patients will be screened in order to randomise approximately 224 patients (with a minimal number of 56 PF procedures) and have 202 evaluable patients age ≥ 18 years, both genders, to

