7.3 Procedures for Day 0 Treatment (Pre-operative)

- Re-assess patient to confirm that the patient is ready for surgery and meets the pre-operative inclusion criteria and none of the exclusion criteria. No changes in health status have occurred between the initial screening and the day of surgery that would affect the patient and/or study conduct.
 - Record medical history, physical examination results, an assessment of neurological status, vital signs, and weight.
 - Perform a urine screening for pregnancy test (for women of childbearing potential). If screening occurred more than 48 hours prior to performing the operation, baseline clinical laboratory values (see [Appendix 4](#)) will be measured.
 - Record AEs.
-
- 

- Record concomitant medications and non-drug therapies.
- Perform pre-operative randomisation (surgeon remains blinded to treatment until intra-operative screening is complete, as described in Section 7.4)

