6. STUDY POPULATIONS

6.1 Subject Disposition

The number of subjects who signed informed consent (enrolled), met the pre- and intra-operative inclusion and exclusion criteria (eligible), were randomized, and withdrew early will be displayed for subject disposition. Early withdrawals will be summarized according to reason for withdrawal. Subjects who have been assigned a treatment based on pre-operative criteria, but were found not eligible intraoperatively are not considered to be randomized (for more detail on randomization see section 5.4).

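### The Synopsis randomises after a confirmed leak but Sections 5.2 and 7.3 assign treatment before surgery; only the operating surgeon and the patient are kept blind during intra-operative screening, and unused assignments are not reported by arm

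*Protocol*

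**What the plan says.** The documents give two moments for randomisation.

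- **After the leak.** In the Protocol Synopsis (Study Design), and only if a leak is confirmed, "the patient will be randomised to treatment with either FS VH S/D 500 s-apr or DuraSeal Dural Sealant (control) in a 1:1 allocation ratio".
- **Before surgery.** Protocol 5.2 states that "upon confirmation of pre-operative eligibility criteria, a member of the site study staff other than the surgeon will obtain a treatment assignment". Protocol 7.3 lists, among the pre-operative steps, "Perform pre-operative randomisation (surgeon remains blinded to treatment until intra-operative screening is complete". SAP 5.4 repeats the 5.2 procedure.

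Protocol 3.1 and 3.2 and SAP 5.1 speak of applying the assignment when a leak is found, which fits either timing.

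Protocol 5.6 blinds the patient throughout and the operating surgeon until the intra-operative entry criteria are confirmed. It describes investigators, surgery personnel and site study personnel as not blinded. Section 5.2 also provides that "Adequate amounts of FS VH S/D 500 s-apr and DuraSeal Dural Sealant will be taken into the operating room".

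If the patient fails in theatre, Section 5.2 requires the failed criterion, date and reason in the eCRF, and "an entry will be made in the IWRS that the study treatment was not administered". SAP 6.1 adds: "Subjects who have been assigned a treatment based on pre-operative criteria, but were found not eligible intraoperatively are not considered to be randomized". The full analysis set and the safety set both require treatment (Protocol 9.3; SAP 6.2).

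**The concern.** When assignment comes before the last eligibility screen, anyone who knows the arm and can influence that screen can affect who enters each arm. Three intra-operative inclusion criteria and nine exclusion criteria are applied after the assignment exists (Protocol 4.3). Several call for judgement: whether the dural cuff is adequate, whether the gap exceeds 2 mm, whether any other finding precludes the study procedure, and whether a leak is seen. The gap criterion is left to the investigator, who need not be the operating surgeon. The Valsalva manoeuvre that can reveal the qualifying leak is performed by the anaesthesiologist (Protocol 5.3.3), who would ordinarily count as surgery personnel.

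If patients at high risk of leakage were screened out more often in one arm, the comparison would be biased. In a non-inferiority trial, losing poor-prognosis patients from the test arm favours the claim. Patients dropped at this step fall outside the randomised count and every analysis set, so the planned tables would give no sign of it.

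**Working it through.** **1. Passages side by side.** Protocol 5.2, 7.3 and 7.4 and SAP 5.4 and 6.1 describe one procedure: assign before surgery, screen in theatre, then reveal to the surgeon. The Synopsis describes another: screen in theatre, then randomise. The difference decides who counts as randomised, so it is more than a matter of style.

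**2. The plan's own figures.** Protocol 9.2 needs 202 evaluable patients, 101 per arm, with a 10% loss to the per-protocol set. 101/0.9 = 112.2, stated as 112 per arm and 224 in total; 224 × 0.9 = 201.6. The stated 224 is reproduced. Protocol 4.1 says: "Approximately 476 patients will be screened in order to randomise approximately 224 patients". The implied overall screen failure is (476 − 224)/476 = 252/476 = 52.9%. The planned screen-failure rate itself is redacted.

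**3. Unused assignments under 5.2 and 7.3.** Let f be the share of the 476 who fail before an assignment is obtained. The documents do not give f, so it is varied here as an assumption. The 224 is taken in the SAP 6.1 sense, as patients who also passed the intra-operative screen.

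Assignments issued = 476(1 − f); unused share = 1 − 224/[476(1 − f)].

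| f (assumed) | issued | unused | unused share |
|---|---|---|---|
| 0% | 476 | 252 | 52.9% |
| 10% | 428 | 204 | 47.7% |
| 20% | 381 | 157 | 41.2% |
| 30% | 333 | 109 | 32.8% |
| 40% | 286 | 62 | 21.6% |
| 50% | 238 | 14 | 5.9% |

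Under the Synopsis timing, about 224 assignments are issued and none is lost to intra-operative ineligibility.

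**4. How sensitive the test is (illustration only).** Inputs: control success 90.6% (Protocol 9.2.1), a true FS rate exactly at the margin (80.6%), 101 per arm, one-sided 2.5%. Suppose a share s of would-be failures is screened out after assignment in the FS arm alone, with those patients replaced.

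Apparent FS rate p = 0.806/[0.806 + 0.194(1 − s)].

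Type I error = Φ[(p − 0.906 + 0.10)/SE − 1.96], with SE = √{[0.906 × 0.094 + p(1 − p)]/101}.

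| s | p | type I error |
|---|---|---|
| 0% | 80.6% | 2.5% |
| 10% | 82.2% | 5.2% |
| 20% | 83.9% | 10.3% |
| 30% | 85.6% | 19.4% |

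Exact enumeration gives about 2.8%, 5.7% and 11% for the first three rows. The calculation ignores covariate adjustment and the interim look. It shows what selective exclusion would do, not that it will happen.

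**The case against.** The strongest reply is that the person who makes most of these calls does not know the arm. The operating surgeon is blinded until eligibility is confirmed, someone else obtains the assignment, and having both products in theatre gives nothing away. This is a real safeguard, and it reduces the concern to leakage of the assignment from other staff. The statement in 5.6 that those staff are unblinded might be meant for the period after treatment, but nothing in the text conceals the assignment from them earlier.

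It can also be said that the Synopsis is the outlier and correcting it would remove the inconsistency. That is true of the wording, but it would leave the concealment and reporting gaps.

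Three stronger readings are tempting and are not supported:

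- **A reader might infer that about half of all assignments are thrown away on subjective grounds by people who know the arm.** The 53% counts every screen failure, including failures before surgery. Protocol 4.1 bases its screen-failure estimate on literature using a similar leak-detection method, which points to absence of a leak as the main reason. Other criteria, such as Gliadel placement or two or more dural defects, are largely factual.
- **A reader might infer an open-label trial at this step.** It is single-blind, and the operating surgeon is also blind until eligibility is settled.
- **A reader might infer damage to stratified balance or power.** With assumed blocks of 4 and 25 centres by 2 regions, simulated mean arm-size difference rises from about 5 to 9 patients if unused slots are lost, but stays at about 5 if they are reused. The documents do not say which applies, and they mention both dynamic allocation (5.2) and flexible random blocks (5.6). Any power loss would be negligible.

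Finally, the data are not lost. The eCRF and IWRS entries are required, and the SAP does not forbid a display by arm. It simply does not ask for one.

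**Conclusion.** The concern holds in this limited form. The Synopsis conflicts with Protocol 5.2 and 7.3 and SAP 5.4 on when randomisation occurs. Under the pre-operative procedure, concealment during the intra-operative screen is specified only for the operating surgeon and the patient. The planned disposition lists enrolled, eligible, randomised and withdrawn patients, so it would not reveal exclusions that differ by arm. The number of unused assignments is unknown: between 0 and 252, at most 53% of those issued, and probably mostly for absence of a leak, which is an inference from Protocol 4.1. The risk is selection bias through leakage of the assignment. The documents contain no evidence that it will occur. The type I error figures depend on the assumed pattern of exclusion and show only that modest selective exclusion would matter. The point is worth an amendment but does not invalidate the design.

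**What to change.** **Preferred.** Amend Protocol 5.2, 7.3 and 7.4 and SAP 5.4 so that the IWRS releases the assignment only after all intra-operative criteria and the leak have been recorded, as the Synopsis states. The cost is a protocol and IWRS change, a short IWRS call in theatre, and possibly some FS thawed but not used. Section 5.2 says both products are brought in, not that FS is thawed for every patient. Appendix 6 gives about 85 minutes for thawing, and Section 5.11 limits use to 4 hours with no refreezing.

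**If pre-operative assignment is kept.** Correct the Synopsis, and state in 5.2 and 5.6 that the assignment is concealed from all operating-room staff until eligibility is recorded, and how. The cost is wording and a site procedure.

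**In either case.** Amend SAP 6.1 and Table 14.1.1 to show issued but unused assignments by assigned arm, with reasons. The eCRF and IWRS entries required by Section 5.2 already provide the data, so the cost is one additional block in a table.
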